**IND Phase**

Phase I

**Objectives**

Primary Objective:

- To determine and evaluate the safety, tolerability, and feasibility of intra-vaginal administration of Artesunate, administered via vaginal suppository, in healthy women with cervical intraepithelial neoplasia (CIN2/3)

Secondary and Exploratory Objectives:

- To measure the effect of intra-vaginal topical Artesunate administration on histology, based on the regression of CIN2/3 at study week 15, assessed as either CIN1 or no CIN lesion detected by colposcopy/biopsy and cytology.
- To evaluate clearance of HPV as assessed by Hybrid Capture 2 DNA testing of cytologic specimens
- To evaluate the local tissue immune response
- To correlate measures of immune response with clinical response

**Study Population**

Women, 18 years and older, with biopsy-confirmed CIN2/3, and a visible lesion after biopsy.

**Inclusion/  
Exclusion  
Criteria**

Inclusion

- ≥ 18 years
- Capable of informed consent
- HPV-positive by DNA test
- Histologically confirmed CIN2, CIN3, or CIN2/3
- Body weight ≥ 50 kg
- Immune competent

[figure not shown]

	
Exclusion
 

• Pregnant and nursing women

• HIV seropositive

• Active autoimmune disease

• Taking immunosuppressive medication

• Evidence of concurrent adenocarcinoma in situ

• Concurrent malignancy except for nonmelanoma skin lesions

Investigational Treatment	Intra-vaginal administration of Artesunate suppositories, one to three multi-day dosing cycles; 50-200 mg, once a day for 5 days per treatment cycle; prior to scheduled LEEP or cone excisional procedure (standard of care for CIN2/3 patients)
Clinical Study Sites	Johns Hopkins Hospital Greater Baltimore Medical Center (Johns Hopkins Clinical Research Network Site)
Study Design*	Phase I open-label dose escalation study of intravaginal Artesunate, formulated in suppositories, in adult females with biopsy-confirmed CIN2/3. Thirty (30) subjects will undergo up to a total of three cycles of intravaginal Artesunate. The first cycle will be initiated on Day 0, the second at Week 2, and the third and final cycle at week 4. The lowest dose cohort that demonstrates most evidence of clinical efficacy as determined by clinical endpoints will be expanded. A schematic overview of the study design is provided on the next page, including study arms, sample size and schedule of interventions. An outline of scheduled visits and assessments is presented below.
Evaluation Criteria	Safety: Subjects will be monitored for local and systemic adverse events.  Efficacy: Histology, cytology, and HPV PCR at study week 15.
Number of Subjects	A total of 30 patients will be enrolled in this study
Estimated Patient Enrollment Period	12 months after the approvals of IND and JHH IRB

**Subject Participation Duration** 41 weeks from the first dosing

**Statistical Analysis Plan** Statistical analysis will be primarily descriptive due to the small sample size. Treatment related safety and efficacy attributes will be analyzed using the Chi-square test. Any exploratory inferences with a p-value of  $\leq 0.10$  will be considered for further study in subsequent trials.

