**Schematic of Study Design:**

There will be 4 treatment cohorts, which will be filled sequentially

Cohort	Number of patients	Dose	Treatment cycles
I	3	50 mg	1 (5 days)
II	9	200 mg	1 (5 days)
III*	9	200 mg	2 (5 days each)
IV**	9	200 mg	3 (5 days each)

\*\*\*According to the standard of care clinical practice, a postoperative visit will be done 4 weeks after the cone resection.

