#### **5.0 RATIONALE FOR CLINICAL TRIAL DESIGN**

This trial is a prospective, open, dose-escalation study of topical Artesunate, formulated as a suppository, administered intravaginally, prior to standard therapeutic resection of the squamocolumnar junction at study week 15. An initial dose cohort of 3 subjects will receive intravaginal Artesunate for one 5-day treatment cycle. Based on clinical experience with Artesunate, we expect that absorption in the cervical mucosa, which is stratified squamous epithelium, will be less than what is observed with rectal administration, which is a single layer of glandular epithelium. Because cervical stroma is much less vascularized than colorectal stroma, we also expect significantly lower systemic levels of Artesunate in subjects receiving intravaginal dosing. The goal of topical administration is to achieve local, mucosal distribution of study drug, as opposed to systemic levels.

If we do not observe untoward side effects, including mucosal excoriation, in the first dose cohort, we will proceed with dose-escalation. The subsequent cohort will undergo two cycles of treatment, spaced at 2-week intervals. The final cohort will undergo a total of three cycles of treatment, spaced at 2-week intervals. All subjects will undergo an interval colposcopic exam at study week 6. At week 15, if there is still a colposcopically detectable lesion, subjects will undergo standard therapeutic resection. If no lesion is obvious, a biopsy will be taken at the site of the original lesion. The cohort receiving the fewest cycles of Artesunate, and showing therapeutic effect will be expanded (see Section 12 for details). At each vaginal exam, cervical swabs will be obtained and cryopreserved. Peripheral blood will be obtained by venipuncture at baseline, and at study weeks 5, 15, and 28, 41, and the postop visit, and will be cryopreserved for assessment of biomarkers.

This clinical cohort, healthy subjects with colposcopically-directed, biopsy-confirmed CIN2/3, was selected for safety reasons. The study protocol window (15 weeks), is within the standard of care. In pregnant women who have a cervical HSIL, the standard of care is to follow colposcopically until postpartum [7]. We and others have reported that the probability that CIN2/3 will progress in this timeframe is essentially zero [63]. In fact,

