### 10.3 Description of Study Visits

All clinically relevant data collected during the study procedures must be recorded first in the patient file. These data will then be transcribed into the CRF. All visits will be outpatient visits.

At the initial screening visit, in addition to undergoing a standard of care colposcopic evaluation, we will obtain cervical brush specimens for HPV typing, and peripheral blood specimens to determine HLA phenotype, HIV status, and immunologic studies. Subjects with biopsy-confirmed CIN2/3 will be enrolled into treatment cohorts as depicted in Table 4 below.

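### The Synopsis total of 30 patients omits the 12-patient expansion in Section 12.1 (30 + 12 = 42), and its 12-month enrolment period does not fit the stated 20-25 patients a year

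*Combined protocol and SAP*

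**What the plan says.** The Number of Subjects row of the Synopsis reads "A total of 30 patients will be enrolled in this study". The Study Design row repeats the number ("Thirty (30) subjects will undergo up to a total of three cycles of intravaginal Artesunate") and adds, without a count, "The lowest dose cohort that demonstrates most evidence of clinical efficacy as determined by clinical endpoints will be expanded". The enrolment period is given as "12 months after the approvals of IND and JHH IRB".

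The schematic in the Synopsis says "There will be 4 treatment cohorts, which will be filled sequentially" and lists Cohorts I to IV with 3, 9, 9 and 9 patients. Table 4 lists the same four. Section 10.3 says "Subjects with biopsy-confirmed CIN2/3 will be enrolled into treatment cohorts as depicted in Table 4 below". Neither table has a row for an expansion.

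Section 5.0 also says that one cohort will be expanded and refers to Section 12. Section 12.1 supplies the detail: after escalation one level is chosen from levels II-IV, and 12 patients are then enrolled and treated at it. The same section gives 39 as the maximum for escalation alone and an anticipated accrual of 20-25 patients a year, based on experience at one institution. Sections 12.1 and 13.1 both say that dropouts are replaced.

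**The concern.** The Synopsis promises an expansion but states a total that leaves no room for one. Anyone working from the stated total (IRB, monitors, pharmacy) could read 30 as the enrolment limit.

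- If 30 is enforced after full escalation, the expansion cannot take place, and the selected level ends with 9 patients rather than 21.
- If Section 12.1 is followed, the study enrols 12 patients beyond its stated total, although Section 15.1 allows no departure from the protocol without prior written IRB approval.

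The timeline has a separate problem: at the plan's own accrual rate, 12 months is too short even for 30 patients.

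**Working it through.** **Inputs.** Cohort sizes 3, 9, 9, 9 (schematic; Table 4; Section 12.1). Add-on of 3 patients at a level with exactly one DLT among 9 (Section 12.1, step 3). Stated escalation maximum 39, expansion 12, accrual 20-25 a year (Section 12.1). Stated total 30 and enrolment period 12 months (Synopsis).

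**Reproducing the plan's figures.**
- 3 + 9 + 9 + 9 = 30. This matches the Synopsis, with all 30 used by Cohorts I-IV.
- 3 + 12 + 12 + 12 = 39. This matches the escalation maximum, with the add-on used at each of levels II-IV.

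Both sums are right. The fault is that 30 is labelled as the total for the study.

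**Total with the expansion.**
- All four cohorts filled, no DLT: 30 + 12 = 42. Understatement 12/30 = 40%.
- Patients at the selected level: 9 + 12 = 21, against 9 without the expansion.
- If the stated escalation maximum stands: 39 + 12 = 51.
- Escalation stops at Cohort III and Cohort II is expanded, no add-ons: 3 + 9 + 9 + 12 = 33.
- Escalation stops at Cohort II with no safe 200 mg level: 3 + 9 = 12, no expansion.

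So 30 is neither a fixed total nor a maximum. All of these figures are before dropout replacement, for which the plan gives no rate.

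**Accrual time** = N / (patients per year) × 12 months.

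| N | at 25 a year | at 20 a year |
|---|---|---|
| 30 | 14.4 months | 18.0 months |
| 42 | 20.2 months | 25.2 months |
| 51 | 24.5 months | 30.6 months |

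**What 12 months yields.** At the stated rate, 20-25 patients.
- Against 30: short by 30 − 25 = 5 to 30 − 20 = 10.
- Against 42: short by 42 − 25 = 17 to 42 − 20 = 22.

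**Rate needed to finish in 12 months.**
- 30 a year for 30 patients: 30/25 = 1.2 to 30/20 = 1.5 times the stated rate.
- 42 a year for 42 patients: 42/25 = 1.7 to 42/20 = 2.1 times.

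If the stated rate excludes the second site, that site would have to supply the shortfall: 5-10 a year for 30 patients, or 17-22 a year for 42.

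These times are lower bounds. Cohorts fill in sequence with a DLT check between them, and the expansion level is generally chosen on Week 15 viral load and lesion data. Any pause in accrual for either adds to them.

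**The case against.** The strongest objection concerns the timeline. The rate rests on experience at one institution, while the Synopsis lists two hospitals and Sections 10.1 and 14.0 give the second its own recruiting investigator and team. If 20-25 is a single-site rate, 30 patients in 12 months needs only 5-10 from the second site, which is plausible. Both figures are also planning estimates: the Synopsis row is headed as estimated, and the rate is described as anticipated. Section 9.0 reports nearly 500 patients recruited for screening over 12 years (500/12, about 42 a year) and expects referrals to grow.

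This makes the timing point conditional but does not remove it. Section 12.1 gives 20-25 as the rate anticipated for this trial; the reference to the institution describes the experience behind the forecast. The plan states no contribution from the second site. The Section 9.0 figure counts recruitment to screening, not patients treated, and the forecast may already reflect it. For 42 patients the second site would need 17-22 a year, close to the whole stated rate.

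On the total, it can be said that Section 12.1 is explicit, so a careful reader would not drop the expansion. That is fair as to the likely harm, but the stated total still conflicts with the section that governs enrolment. Some footnote text is also missing from the copy reviewed: the Study Design row and Cohorts III and IV in the schematic carry markers whose notes are not shown, and those notes might mention the expansion. The Number of Subjects row and Table 4 carry no markers, and both leave it out.

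**Conclusion.** Both parts hold. The 30 in the Synopsis covers the four escalation cohorts only, and the 12 expansion patients are newly enrolled after escalation ends. On the path through Cohort IV with no DLT the planned total is 42, so the Synopsis is short by 12. That figure assumes no add-on patients and no dropout replacement; an early stop would give a different number.

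The 12-month period is inconsistent with 20-25 patients a year for 30 patients and more so for 42. This rests on reading 20-25 as the rate for the whole trial. If it covers one site only, the conclusion depends on a second-site contribution that the plan does not give. Confidence is high on the total; the timing is subject to that reading.

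**What to change.** Reconcile the Synopsis with Section 12.1.

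- **If the expansion stands:** state the total as 30 base escalation + 12 expansion = 42 planned, plus any step 3 add-ons and dropout replacements. Add an expansion row to the schematic and to Table 4.
- **If 30 is the intended total:** explain in Section 12.1 how the 12 expansion patients fit within it.
- **Maximum:** this would be 51 if the escalation maximum of 39 stands. State it only after the escalation steps in Section 12.1 have been reconciled with the stopping rule in Section 11.9, because the add-on patients depend on how the two fit together.
- **Enrolment period:** if 20-25 a year covers both sites, restate the period for 42 patients as at least about 20-25 months, and note that pauses for DLT checks or Week 15 data would lengthen it. Otherwise give the rate that supports 12 months (at least 42 a year for 42 patients) and the second site's share of it.

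The cost is a text amendment to the Synopsis, schematic, Table 4 and enrolment period (or Section 12.1, if 30 is kept), with prior written IRB approval. No patients are added beyond those in Section 12.1. The stated timeline becomes longer unless a higher rate is justified.

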### **7.2 Secondary Outcome Measures**

Indicators of drug efficacy (see below) will be drawn from any evidence demonstrating a significant difference (by simple chi-square analysis;  $p < 0.1$ ) between treated subjects and the baseline data in the Johns Hopkins Colposcopy database

- Extent of lesion clearance (by lesion number, size, and/or area of coverage)
- Presence/absence of HPV DNA
- Regression of CIN stage by histopathology (comparison of initial biopsy to LEEP/cone excision-procured tissue).

Histologic regression will be judged as none (persistent CIN2/3 in week 15 resection specimen) or total (no CIN2/3 in resection specimen).

Virologic HPV viral load. Longitudinally obtained cervical swabs will be used to quantitate HPV viral load as a continuous variable.

Tissue sections from the diagnostic biopsy obtained as part of the screening process, and from the resection specimen obtained post-treatment will be assessed for expression of CD8 (effector T cells), CD71 (transferrin receptor), and cleaved caspase 3 (apoptotic cell death).

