## **12.0 STATISTICAL CONSIDERATIONS**

### **12.1 Study Design/Endpoints/Accrual**

The primary statistical outcome of the trial is safety. The treatment groups will be filled sequentially in a non-blinded manner. Study dropouts will be replaced.

The dose escalation algorithm is described as follows (see Table 4 for dose levels to be tested):

1. A run-in cohort of three patients will be treated with one 5-day cycle of 50mg vaginal suppositories. If no patient has a DLT observed by the cervix check visit after the last suppository, the trial will proceed to the next level.
2. A cohort of 9 patients will be enrolled and treated with one 5-day cycle of 200mg vaginal suppositories. If no patient has a DLT observed by the cervix check after the last suppository, the dose level will be considered tolerable and the trial will proceed to the next level.
3. If exactly one of the 9 patients has a DLT by Week 1-2 after the last suppository, three more patients will be enrolled and treated at the current dose level. If none of the three patients has a DLT by the cervix check after the last suppository, the current dose level will be considered safe and dose will be escalated.
4. If two or more of the 9 or 12 patients have a DLT observed by Week 1-2 cervix check, dose escalation will be stopped. The current dose level will be considered unsafe.
5. A cohort of 9 patients will be enrolled and treated with 2 cycles of 200 mg vaginal suppositories, at 2-week intervals. If no patient has a DLT observed in Cohorts II and III, then the dose level will be considered safe, and the dose will be escalated.
6. A cohort of 9 patients will be enrolled and treated with 3 cycles of 200 mg vaginal suppositories, at 2-week intervals. If no patient has a DLT observed by the cervix check after the last suppository, then the dose level will be considered safe.

With the dose escalation algorithm, there will be less than 9% probability to escalate to the next higher dose level if the DLT rate for the current dose level is 30%.

The maximum sample size for dose escalation is 39. Based on our experience in investigator-initiated therapeutic trials in this patient population at this institution, our anticipated accrual rate is 20-25 patients per year.

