### 12.3 Other Efficacy Endpoints

[figure not shown]
In every case possible, change in lesion size from week 0 to week 15 will be measured using serial digital colpographs. Changes in HPV16 E7-specific T-cell response (CD8) will be compared at week 0 to week 15. Differences will be calculated between baseline and follow-up and the appropriate transform performed. Point estimates, confidence intervals, and hypothesis testing (i.e. paired t-test and signed rank test) will be done.

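### The chi-square test named in the Synopsis and Section 7.2 does not suit sparse by-cohort tables or measured lesion outcomes, and does not match Section 12

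*Combined protocol and SAP*

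**What the plan says.** The statistical entry of the Synopsis (Section 1.0) opens with "Statistical analysis will be primarily descriptive due to the small sample size" and continues: "Treatment related safety and efficacy attributes will be analyzed using the Chi-square test". It then says of later use: "Any exploratory inferences with a p-value of" 0.10 or less will be considered for subsequent trials. It gives no comparison groups, table layout or exact version of the test.

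Section 7.2 names a simple chi-square at p < 0.1 for one stated comparison, treated subjects against the Johns Hopkins Colposcopy database. The first item on its list is "Extent of lesion clearance (by lesion number, size, and/or area of coverage". The other two, HPV DNA status and histologic regression, are binary.

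Section 12 reads differently. In 12.3, "change in lesion size from week 0 to week 15 will be measured using serial digital colpographs", with point estimates, confidence intervals, paired t-tests and signed-rank tests. Section 12.2 uses the same paired tests for viral load. Section 12.4 adds random effects models for viral load and lesion size and a logistic model for regression, compares lesion-size change with an observational cohort without naming a test, and summarises toxicity descriptively. No exact test and no trend test across cohorts is named anywhere.

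**The concern.** Safety has no comparator in the plan, inside or outside the trial, so the natural table for a safety chi-square is event by cohort, with very small rows. The large-sample approximation is poor there, yet 0.10 is the threshold that decides which findings are considered for later trials.

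For lesion number, size and area, a chi-square can be run only after the values are cut into categories. An unspecified cut discards information and leaves a choice that could be made after the data are seen.

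The Synopsis, Section 7.2 and Section 12 also leave an analyst unsure whether toxicity is tested at all, and on what scale lesion change is compared.

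**Working it through.** **Inputs from the documents.** "There will be 4 treatment cohorts, which will be filled sequentially" (study schematic). Cohort sizes are 3, 9, 9 and 9 (schematic and Table 4), total 30: "A total of 30 patients will be enrolled in this study" (Synopsis). The threshold is 0.10. The external cohort has over 250 women (Section 12.4); 250 is used below. The size of the colposcopy database in Section 7.2 is not stated. Background regression for HPV16 lesions is 20–25% (Section 5.0).

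**Assumed.** Event and response rates by cohort are not in the documents, so ranges are shown. The plan gives no size or power figure for the chi-square, so there is none to reproduce.

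**1. Expected counts.** With k events among N = 30, a cohort of n has expected counts n·k/30 and n·(30−k)/30, which sum to n. Two numbers that sum to 9 or 3 cannot both reach 5, so every row has at least one expected count below 5 whatever k is. If Section 12.1 enlarges a cohort to 12, both reach 5 only for an overall proportion between 5/12 = 42% and 7/12 = 58%.

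**2. Single-table p-values.** X² = Σ(O−E)²/E on 3 df.

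- One event, in Cohort I. Event cells: 0.9²/0.1 + 3 × 0.3 = 9.0. Non-event cells: 0.9²/2.9 + 3 × 0.3²/8.7 = 0.31. X² = 9.31, p = 0.025. Exact p: 3 of the 30 women are in Cohort I, so 3/30 = 0.10.
- Two events, both in Cohort IV. Event cells: 0.2 + 0.6 + 0.6 + 1.4²/0.6 = 4.67. Non-event cells: 0.2²/2.8 + 2 × 0.6²/8.4 + 1.4²/8.4 = 0.33. X² = 5.00, p = 0.17. Exact p: of C(30,2) = 435 placements, those at least as extreme are both events in one of II–IV (3 × 36 = 108), both in I (3), or one in I and one elsewhere (3 × 27 = 81). That is 192/435 = 0.44.

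**3. Overall error rate.** All 4 × 10 × 10 × 10 = 4,000 tables were enumerated with binomial probabilities under a common rate, rejecting at p ≤ 0.10.

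| Common rate | Pearson | Exact version of the same statistic |
|---|---|---|
| 2% | 3.6% | 3.6% |
| 5% | 5.2% | 5.0% |
| 10% | 7.0% | 5.5% |
| 25% | 10.2% | 6.2% |

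Pearson is at or below nominal, apart from 0.2 points at 25%. At that rate the two versions disagree about reaching 0.10 in at least 10.2 − 6.2 = 4.0% of trials.

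**4. Treated women against an external group of 250, both at 25%.** Nine women: expected events 9 × 0.25 = 2.25; Pearson size 11.2%, Fisher 5.1%. All 30 pooled: 30 × 0.25 = 7.5; Pearson 9.9%, Fisher 7.6%. Pearson is acceptable when pooled and slightly above nominal for a single cohort.

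**5. Lesion measures.** Section 7.2 puts number, size and area under a chi-square and gives no categories. Section 12.3 takes differences in lesion size, transforms them and tests them as paired values. The same measure is categorical by implication in one place and continuous in the other.

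**6. Cohort order.** Power at 0.10 under assumed rates, Pearson against exact trend:

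| Cohorts and rates | Pearson | Exact trend |
|---|---|---|
| I–IV: 20/30/50/70% | 46% | 63% |
| I–IV: 20/50/50/50% | 14% | 14% |
| I–IV: 20/30/60/40% | 29% | 18% |
| II–IV: 30/50/70% | 45% | 42% |

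An asymptotic trend test reaches 54% in the last row, but it relies on the kind of approximation that is in doubt.

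**The case against.** The defence is that the analysis is declared mainly descriptive and Section 12 already gives suitable methods for viral load, lesion size and regression. The only chi-square with named groups is the external comparison in Section 7.2, where cohort order plays no part and the pooled test is sound. The example p-values also change no call at the Synopsis threshold: 0.025 and 0.10 both meet it, while 0.17 and 0.44 both miss it. Escalation and stopping rest on DLT counts.

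Most of this stands. A reader might infer that chi-square governs every endpoint; Sections 12.2 to 12.4 show otherwise. A reader might also infer that it produces excess false positives overall; step 3 shows that it does not. A third tempting reading is that an ordered test must replace it. The by-cohort table is only one reading of the Synopsis, and step 6 shows that the trend gain needs a monotone pattern across all four cohorts, including the run-in of three. Section 12.1 selects the expansion dose from levels II–IV only, where the exact trend test has no advantage.

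It could further be said that the paired tests in 12.3 and the external comparison in 7.2 answer different questions. That is fair, but the external comparison of lesion measures still has no usable test: 7.2 names one that needs an unstated cut-point, and 12.4 names none.

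**Conclusion.** The point holds in a limited form. By-cohort chi-square p-values in tables of 3/9/9/9 are unreliable one at a time: by a factor of 0.10/0.025 = 4 in one example and 0.44/0.17 = 2.6 in the other. Averaged over tables, the test is about nominal or conservative. The expected-count result and the two worked tables rest on the planned cohort sizes alone; the error rates and powers rest on assumed rates, and step 4 also on an assumed external size of 250.

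Two wording faults need no assumption: lesion number, size and area are placed under a test that does not fit their scale, and the Synopsis tests safety where Section 12.4 only describes it. Severity is low to moderate, since the tests are exploratory and no escalation decision uses them.

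**What to change.** - In the Synopsis and Section 7.2, state which groups each test compares.
- For binary attributes (HPV DNA status, histologic regression), replace chi-square with Fisher's exact or mid-P tests and report exact confidence intervals.
- Analyse lesion number, size and area on the measured values: paired tests within subject as in Section 12.3, and rank or regression methods against the external cohort. Name that test in Section 12.4 as well.
- Describe toxicity by cohort with exact intervals and remove the safety chi-square, so that the Synopsis agrees with Section 12.4.
- Optionally add an exact trend test across cohorts, labelled exploratory, with scores fixed in advance and the loss under a non-monotone pattern acknowledged.

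The cost is wording plus some conservatism. For 50% against 25% with an external group of 250, Fisher's power is 85% against 87% for Pearson with 30 treated women, and 44% against 51% with nine. Mid-P lessens this loss.
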